8.0 STATISTICAL CONSIDERATIONS

8.1. Overview

The primary objective of this study is to assess the safety and tolerability of cAd3 Marburg at two dose levels. The secondary objective is to evaluate the antibody and Marburg GP-specific T-cell responses to the GP insert and cAd3 vector at 4 weeks after vaccination. An exploratory evaluation of immunogenicity, including assays with samples collected at different study timepoints, profiling vaccine-induced mRNA expression, isolating MAbs to determine epitope specificity, and evaluating plasmablasts to follow lineage development of anti-GP antibodies, will also be performed. A total of 40 participants will be enrolled with 20 to receive a 1×10^{10} PU/mL dose and 20 to receive a 1×10^{11} PU/mL dose of the cAD3-Marbug and followed through 48 weeks post-vaccination.

8.2. Sample Size and Accrual

8.2.1. Power and Sample Size Calculations for Safety

The goal of the safety evaluation for this study is to identify safety concerns associated with vaccination. Occurrence of solicited local and systemic reactogenicity symptoms, occurrence of adverse and serious adverse events will be assessed as the proportion of participants experiencing such safety event. Table 4 below shows 95% confidence intervals for 0, 1, 2, 5, and 10 participants with observed events in each group or among all study participants.

Table 4: Exact 95% Confidence Intervals for the Proportion of Participants Experiencing a Safety Event

| Group | Sample Size | Number of Participants with an Event(s) Observed | | | | |
|-----------------------------|-------------|--|-----------------------|---------------------|-----------------------|----------------------|
| | | 0 | 1 | 2 | 5 | 10 |
| Each Individual Study Group | 20 | 0% (0%-16.8%) | 5% (0.1%-24.9%) | 10% (1.2%-31.7%) | 25% (8.6%-49.1%) | 50% (27.2%-72.8%) |
| All participants | 40 | 0% (0%-8.8%) | 2.5% (0.06%-13.2%) | 5% (0.6%-16.9%) | 12.5% (4.2%-26.8%) | 25% (12.7%-41.2%) |

If no participants experience an event, the upper limit of a two-sided exact 95% CI would be 16.8% for an individual group and 8.8% for the entire study group. While this study is not necessarily powered to detect differences between groups, we would have 82% power to detect a difference of 40% ($p_1=0.1$ and $p_2=0.5$) using Barnard's exact unconditional test at a 5% two-sided level of significance.

Changes in laboratory measures from baseline will also be described. For continuous safety measures, Table 5 below shows minimum detectable changes from baseline to a specified time point using a paired t-test with a two-sided 5% level test.

Table 5: Minimum Detectable Differences, in Standard Deviations, for Change From Baseline to a Single Time (2-sided $\alpha=0.05$)

| Group | Sample Sizes | Power | | |
|-----------------------------|--------------|-------|------|------|
| | | 80% | 85% | 90% |
| Each Individual Study Group | 20 | 0.66 | 0.71 | 0.76 |
| All participants | 40 | 0.45 | 0.49 | 0.53 |

If comparing the two study groups, we would have 80% power to detect a difference of 0.91 standard deviations using a two-sample t-test at a two-sided 5% alpha and assuming equal variances.

8.2.2. Power and Sample Size Calculations for Immunogenicity

The precision and power calculations for safety shown in Table 4 and Table 5 also apply to immunogenicity results. Results of immunogenicity assessments can be shown as proportion of responders (Table 4) or continuous measures (Table 5). For example, if we observe 10 positive responses from an ELISA assay in an individual group, the 95% exact confidence interval of the true response rate will range from 0.272 to 0.728. Note that immunogenicity is a secondary objective for this protocol.

8.3. **Statistical Analysis**

All analyses will be described overall and by vaccination group (Group 1 and Group 2). The safety and immunogenicity analysis will include all vaccinated participants. All statistical analyses will be performed using Statistical Analysis System (SAS), R, or S-Plus statistical software. No formal multiple comparison adjustments will be employed for safety endpoints or secondary endpoints.

8.3.1. Baseline Demographics

Baseline demographics and laboratory measurements will be summarized for individual groups and overall. Categorical variables will be reported in numbers and percents with exact 95% Clopper-Pearson confidence intervals. Continuous variables will be reported in means and standard deviations or medians and IQR as appropriate.

8.3.2. Safety Analysis

Safety and tolerability will be assessed by both clinical and laboratory monitoring. If comparisons are performed between groups, then Barnard's exact unconditional test will be performed for binary variables and t-tests (or Wilcoxon Rank Sum as appropriate) for continuous measures.

Reactogenicity

The number and percentage of participants experiencing each type of reactogenicity sign or symptom will be tabulated by study group and severity. Exact 95% Clopper-Pearson confidence intervals will be calculated for each set of events. For a given sign or symptom, each participant's reactogenicity will be counted once under the maximum severity for all assessments.

Adverse Experiences

Adverse experiences are coded into Medical Dictionary for Regulatory Activities (MedDRA) system organ classes and preferred terms. The number and percentages of participants experiencing each specific adverse event will be tabulated by dose level, severity and relationship to treatment. For the tabulation of the adverse experiences by system organ class, a participant was counted only once in a given body system. For example, a participant reporting gastritis and diarrhea will be reported as one participant, but the symptoms will be listed as two separate AEs within the class. A complete listing of adverse experiences for each participant will provide details including preferred term, system organ class, severity, relationship to treatment, onset time, duration and outcome.

Local Laboratory Values

Boxplots of local laboratory values will be generated for baseline values and for values measured during the course of the study. Each boxplot will show the 1st quartile, the median, and the 3rd quartile. Outliers, or values outside the boxplot, will also be plotted. If appropriate, horizontal lines representing boundaries for abnormal values will be plotted. Tables will be provided for changes from baseline.

8.3.3. Immunogenicity Analysis

Immunogenicity analysis will consist of all vaccinated participants. If assay data are qualitative (i.e., positive or negative) then analyses will be performed by tabulating the frequency of positive response for each assay at each timepoint that an assessment is performed. Binomial response rates will be presented with their corresponding exact 95% confidence interval estimates. Barnard's exact unconditional tests will be used to compare the two groups to each other. For quantitative results, mean and standard deviation will be calculated. One-sample t-tests will be used to assess the changes from baseline. Two-sample t-tests will be used to compare the two study groups. Missing responses will be assumed to be missing at random, i.e., conditional on the observed data the missingness is independent of the unobserved responses. Graphical descriptions of the longitudinal immune responses will also be given.

Some immunologic assays have underlying continuous or count-type readout that is often dichotomized into responder/non-responder categories. For these assays, graphical and tabular summaries of the underlying distributions will be made. These summaries may be performed on transformed data (e.g., log transformation) to better satisfy assumptions of symmetry and homoscedasticity.

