2.2. Secondary Objectives

- To evaluate the antibody responses to the GP insert and cAd3 vector in VRC-MARADC087-00-VP at 4 weeks after vaccination as assessed by GP ELISA and vector-specific neutralization assays, respectively.
- To evaluate the Marburg GP-specific T cell responses in VRC-MARADC087-00-VP at 4 weeks after vaccination as assessed by ICS.

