3.2. Secondary Endpoints: Immunogenicity

Antibody titers, response rates and magnitudes will be the immunogenicity endpoints for the following assays where relevant: ELISA and antigen-specific and vector-specific neutralization assays and ICS assays for T cell responses. The principal time point for assessing antibody and T cell responses is Week 4 after vaccination.

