4.0 STUDY DESIGN AND METHODS

This is a Phase I open-label, dose escalation clinical trial to evaluate the safety, tolerability and immunogenicity of cAd3-vectored vaccines for Marburg WT GP in healthy adults. The study will be conducted at the WRAIR CTC in Silver Spring, Maryland, USA.

Twenty participants will be enrolled in each of the two dosage groups for cAd3-Marburg. The study will begin with enrollment of 3 participants into Group 1. After at least 7 days of follow-up for the first 3 vaccinated participants, an interim safety review will occur before enrollment of additional participants into the group. If no safety issues are identified, an additional 17 participants will be enrolled to complete Group 1. When there is a minimum of seven days of follow-up safety data from the last enrolled participant in Group 1, an interim safety review will occur. Once no safety issues are identified, enrollment of participants into the next dose level will begin with the enrollment of 3 participants. After at least 7 days of follow-up for the first 3 vaccinated participants in Group 2, an interim safety review will occur before the enrollment of additional participants into Group 2. If no safety issues are identified, an additional 17 participants will be enrolled to complete Group 2. For the first 3 participants in each group, only one participant per day will be enrolled.

Study agent administration will be on Day 0. The study includes daily review of any new safety data by a study clinician and weekly review of safety data by the Protocol Safety Review Team (PSRT). The staged enrollment plan and plan for interim safety reviews (Section 7.3) applies to both Group 1 and Group 2. The interim safety reviews will be conducted by the PSRT.

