5.1.2. Consent Procedures and Screening

Following the briefing sessions, volunteers who remain interested in the study will be scheduled for a screening visit. At the beginning of the screening visit, written informed consent will be obtained from the volunteer by the PI or their designee. Written informed consent will be obtained from each participant before any study procedures are performed. All informed consent forms will be administered individually, in a private setting, with strict respect of confidentiality. Participants will be given ample time and opportunity to inquire about details of the study, discuss with close family members or friends and ask any questions before dating and signing the consent forms. A copy of the signed informed consent form will be given to the participant along with a copy of the volunteer event schedule (Appendix 5). The consenting process will be documented in the case report forms (CRFs).

After providing signed informed consent the volunteer will complete an AOU. Volunteers are allowed to take the AOU three times, but must have a passing score (90% or greater) by the third attempt to participate in the study. If after 3 attempts to pass the AOU the volunteer is unable to do so, the volunteer will become ineligible for study participation. Volunteers who successfully pass the AOU will then be screened as per the study protocol.

Volunteers who have passed the AOU and have given written informed consent will undergo a complete medical history, physical examination, and screening laboratory assessments to determine eligibility for trial participation. The following screening assessments will be completed after the informed consent process has been completed:

- Medical history
- Physical exam
- Vital signs and weight
- Serum (or urine if screening is the same day enrollment) pregnancy test for all females
- CBC with total lymphocyte count
- Creatinine
- ALT
- HIV testing (including pre/post-test counseling)
- Syphilis testing
- Pre-existing vector immunity testing
- Serum storage for antibody assays
- Peripheral blood mononuclear cells (PBMC) and plasma for storage

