Screening evaluations for specific eligibility criteria (see Sections 4.1.1 and 4.1.2) must be completed within the screening visit window specified (Appendix 1) prior to enrollment, but may be repeated, if the initial laboratory result is not deemed medically significant, within the screening visit window in order to confirm eligibility. Samples for storage may also be collected within the screening visit window. Counseling on the potential risks of becoming pregnant during study participation will be provided. Pre-HIV test counseling and post-HIV test counseling will be provided during the screening process.

Study volunteers may be scheduled for a second Screening Visit to evaluate laboratory and test results if an abnormality or illness had been identified at the first screening. This approach will allow study staff to evaluate the recovery from any illness identified at the first screening as well as to repeat screening laboratory tests that were abnormal at the first screen due to transient illness.

Eligible and willing volunteers will be scheduled for an appointment for enrollment and the initial vaccination visit within 56 days of having satisfied eligibility requirements.

5.1.3. Day 0 Through Week 48

Day 0 is defined as the day of protocol enrollment and the study injection. Study eligibility criteria are reviewed on Day 0 as part of the enrollment process. If clinical assessment on Day 0 suggests significant changes may have occurred since the screening visit, then the physical examination, hematology tests, blood chemistries, and urinalysis done at screening must be repeated, as appropriate, before the participant receives the experimental vaccine. Pregnancy test results for women of childbearing potential must be obtained prior to the study injection. Day 0 evaluations immediately prior to the first injection are the baseline for subsequent safety assessments.

Refer to the table in Appendix 1 for details on the SOE and the window(s) permitted. After Day 0, deviations from the visit windows in completing study visits are discouraged and will be recorded as protocol deviations, but are permitted, at the discretion of the PI (or designee), in

consultation with the sponsor, in the interest of obtaining participant safety and immunogenicity evaluations following exposure to the investigational vaccine.

Study visit procedures and tests through Week 48 include the following as indicated in the SOE (Appendix 1):

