9.0 SAMPLE AND DATA MANAGEMENT

9.1. Plan for Use and Storage of Biological Samples

9.1.1. Use of Samples, Specimens and Data

Samples, specimens and data collected under this protocol may be used to conduct protocol-related safety and immune response evaluations, exploratory laboratory evaluations related to the type of infection the study agent was designed to prevent, exploratory laboratory evaluations related to vaccine or infectious disease research in general and for research assay validation. Genetic testing will be performed in accordance with the information included in the study informed consent for genetic testing (Appendix 2C). Results from genetic testing will not be provided to participants as the test results are not validated for clinical use. Safety labs may be completed by Quest Diagnostics Inc.

Immunogenicity of the VRC-MARADC087-00-VP vaccine will be evaluated as humoral and cellular immune responses assessed by ELISA and intracellular cytokine staining (ICS) assay. Other measures of immunogenicity may be also conducted as exploratory evaluations. The ELISA assay will be performed at the VRC or VIP and the exploratory evaluation of Marburg-specific neutralizing antibodies will be conducted at the VRC, using previously published methods [12]. The pre-existing and post-vaccination presence of cAd3 neutralizing antibody also will be evaluated [27]. The ICS assay quantitates the frequency of CD4⁺ and CD8⁺ cells that produce interleukin-2, interferon-gamma and/or tumor necrosis factor in response to pools of overlapping peptides representing Marburg GP antigens and is based upon previously published methods [30].

Other measures of immunogenicity may be conducted as exploratory evaluations. Specific peptides may be used to detect T-cell responsiveness by an enzyme-linked immunospot (ELISpot) assay, modified from a previously published method [31]. Genetic factors associated with immune responses may also be evaluated; isolation of MAbs to determine epitope specificity and function capacity may be performed; and time courses of immune responses may be analyzed including durability of cAd3 neutralizing antibody titers, mediators of inflammation following vaccination, and, for the first week, vaccine-induced mRNA expression profiles and plasmablasts to follow lineage development of anti-GP antibodies.

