APPENDIX 1: SCHEDULE OF EVALUATIONS

| RV 507 Schedule of Evaluations | | | | | | | | | | | | | |
|--|------------------------|------------|------------|------------|------------|------------|------------|------------|------------|------------|------------|--|--|
| Visit | 01 | 02 | 02A | 02B | 02C | 02D | 03 | 04 | 05 | 06 | 07 | | |
| Week of Study | -8 to 0 | W 0 | W 1 | W 1 | W 1 | W 2 | W 4 | W 8 | W 16 | W 24 | W 48 | | |
| Day of Study | -56 to 0 | D 0 | D 1 | D 3 | D 7 | D 14 | D 28 | D 56 | D 112 | D 168 | D 336 | | |
| Clinical Evaluations | Screening ¹ | Enrollment | | | | | | | | | | | |
| RV 507 AoU, Informed Consent | X | | | | | | | | | | | | |
| Physical exam and weight at screen; Vital signs, targeted exam at other visits. | X | X | X | X | X | X | X | X | X | X | X | | |
| Medical history for eligibility at screen; interim history other visits | X | X | X | X | X | X | X | X | X | X | X | | |
| Study Vaccination ² | | X | | | | | | | | | | | |
| Begin/Review 7-Day Diary Card | | X | X | X | X | | | | | | | | |
| Telephone contact; clinic visit if indicated | | | | | | | | | | | | | |
| Counseling on pregnancy prevention | X | X | | | | X | X | X | X | | | | |
| CBC w/total lymphocyte count | 3 | 3 | 3 | 3 | | 3 | 3 | 3 | | 3 | 3 | | |
| Pregnancy test: urine (or serum) ³ | 2 | X | | | | | X | | | | | | |
| Creatinine and ALT | 4 | 4 | 4 | 4 | | 4 | 4 | 4 | | | | | |
| HIV ⁵ and RPR | 11 | | | | | | | | | | | | |
| Research Immunology | | | | | | | | | | | | | |
| Serum storage for antibody assays | 12 | 12 | 12 | 12 | 12 | 12 | 12 | 12 | 12 | 12 | 12 | | |
| Pre-Existing Vector Immunity testing | X | | | | | | | | | | | | |
| PBMC and plasma for storage | 30 | 80 | | | 60 | 40 | 80 | 60 | 60 | 80 | 80 | | |
| Intracellular RNA | | 3 | | 6 | 6 | | | | | | | | |
| HLA type ⁴ | | | | | | | | 10 | | | | | |
| Daily Volume (mL) | 62 | 102 | 0 | 25 | 78 | 59 | 99 | 89 | 72 | 95 | 91 | | |
| Max. Cumulative Volume (mL) | 62 | 164 | 164 | 189 | 267 | 326 | 425 | 514 | 586 | 681 | 773 | | |

Visit windows: 02A (+1 day); 02B (+2 days); 02C (+3 days); 02D (±3 days); Visits 03 and 04 (±7 days); Visits 05, 06 and 07 (±14 days).

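### The between-group t-tests in Sections 8.3.2 and 8.3.3 leave out baselines that are already collected; a baseline-adjusted comparison would be a cheap, modest gain in efficiency

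*Combined protocol and SAP*

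**What the plan says.** Section 4.0 describes staged escalation. After Group 1 is full and its safety review is clear, "enrollment of participants into the next dose level will begin with the enrollment of 3 participants". No randomisation is described.

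For quantitative immunogenicity results, Section 8.3.3 tests within-group change from baseline with one-sample t-tests, then says "Two-sample t-tests will be used to compare the two study groups". Section 8.3.2 provides t-tests, or Wilcoxon rank sum tests where suitable, for continuous safety measures if groups are compared at all. Neither section includes a covariate.

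Baselines are available:

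- Section 5.1.2 lists "Pre-existing vector immunity testing" among the screening assessments, and Section 9.1.1 adds that "The pre-existing and post-vaccination presence of cAd3 neutralizing antibody also will be evaluated".
- Appendix 1 schedules "Serum storage for antibody assays" at screening, at Day 0 and at later visits. Blood count, creatinine and ALT are also drawn at screening and Day 0.
- Section 5.1.3 states that "Day 0 evaluations immediately prior to the first injection are the baseline for subsequent safety assessments".

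A secondary objective in Section 2.2 is "To evaluate the antibody responses to the GP insert and cAd3 vector in VRC-MARADC087-00-VP at 4 weeks after vaccination". Section 3.2 adds that "The principal time point for assessing antibody and T cell responses is Week 4 after vaccination". Section 3.1 lists change from baseline in laboratory measures among the primary safety endpoints. Section 8.2.1 gives 80% power for a between-group difference of 0.91 SD by two-sample t-test.

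**The concern.** With 20 per group, precision is limited. Where the pre-vaccination value predicts the follow-up value, a comparison that ignores it, or only subtracts it, carries more residual variance than it needs to. The samples are already drawn, so adjustment would cost only analysis text and about one degree of freedom.

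Sequential enrolment adds a second reason. Nothing in the design balances the groups at baseline, so a reader of the dose comparison will want to see baseline cAd3 immunity by group and how far the result moves when baseline is taken into account. What is at stake is the precision and readability of secondary and optional comparisons. No decision rule depends on them.

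**Working it through.** **Inputs from the plan:** 20 per group (Section 4.0); two-sided 5%, 80% power, equal variances, 0.91 SD (Section 8.2.1). **Assumed, because the documents give no figure:** r, the correlation between baseline and follow-up; the proportion p seropositive for cAd3 at baseline; and d, the difference in Week 4 titre between baseline seropositives and seronegatives, in within-status SDs.

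**1. The plan's figure.** The detectable difference is ncp × √(2/20). For the noncentral t with 38 df at 80% power, ncp = 2.8749, so 2.8749 × 0.3162 = 0.909 SD. This agrees with 0.91.

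**2. Cost of one covariate.** With 37 df, ncp = 2.8770, and the variance is inflated by 1 + 1/36. At r = 0: 2.8770 × 0.3162 × √(1 + 1/36) = 0.922 SD. An uninformative covariate therefore moves 0.91 to 0.92.

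**3. Laboratory measures.** Take a t-test on change as the comparator, with equal SDs σ at Day 0 and follow-up. The SD of change is σ√(2(1−r)) and the ANCOVA residual SD is σ√(1−r²). Their ratio is √((1+r)/2). In SDs of change, ANCOVA detects 0.922 × √((1+r)/2):

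| r | ANCOVA | t-test on change |
|---|---|---|
| 0.3 | 0.74 | 0.91 |
| 0.5 | 0.80 | 0.91 |
| 0.7 | 0.85 | 0.91 |
| 0.8 | 0.875 | 0.91 |
| 0.9 | 0.90 | 0.91 |
| 0.95 | 0.91 | 0.91 |

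At a true difference of 0.909 SD of change, ANCOVA power is 93%, 89% and 85% at r = 0.3, 0.5 and 0.7, against 80%.

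**4. cAd3 neutralising titre, tested as the Week 4 value.** ANCOVA detects 0.922 × √(1−r²), so it beats 0.909 only when r exceeds √(1 − (0.909/0.922)²), about 0.17. If the useful baseline information is serostatus, r² = p(1−p)d² / (1 + p(1−p)d²):

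- p = 0.05: r = 0.11 at d = 0.5 and 0.21 at d = 1.
- p = 0.10: r = 0.15 at d = 0.5 and 0.29 at d = 1.

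These values straddle the break-even point. Simulated ANCOVA power with that binary covariate (40,000 runs, effect 0.909 total SD) is 0.797 and 0.811 at p = 0.05, and 0.800 and 0.823 at p = 0.10. The unadjusted t-test gives about 0.80.

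**5. How often the cAd3 covariate is degenerate.** At p = 0.05, the chance of no seropositive among 40 is 0.95^40 = 0.13. The chance that there are seropositives but all in one group is 2 × 0.95^20 × (1 − 0.95^20) = 2 × 0.358 × 0.642 = 0.46. At p = 0.10 the two figures are 0.90^40 = 0.015 and 2 × 0.122 × 0.878 = 0.21. With no seropositive, adjustment does nothing. With seropositives in one group only and a binary covariate, the adjusted dose effect is simply the seronegative-only comparison.

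**The case against.** The strongest reply is that the planned test is valid and correctly powered, and that ANCOVA is a preference. Section 8.2.1 says that power for group differences was not a design aim, Section 8.2.2 notes that immunogenicity is secondary, and laboratory comparisons are conditional in Section 8.3.2. All of that stands and limits the weight of the point. It does not remove a gain that costs one degree of freedom.

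The cAd3 case is also weaker than it looks. Section 1.2.2 reports low seroprevalence and, where antibody is present, low titres; Sections 1.2.1 and 1.2.2 describe little or no pre-existing immunity. A reader might infer a large gain by assuming 20-30% seropositive, where power would reach 94-96% at d = 2. The documents do not support that prevalence. Even at 5-10%, d = 2 would give 86-90%, but the documents give no figure for such a difference. The frequent degenerate cases in step 5 also argue against making the adjusted cAd3 analysis the main one.

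A reader might infer that the plan means the Week 4 value, because Section 3.2 names that time point. This is not established: Section 8.2.2 applies Table 5, a table of change from baseline, to continuous immunogenicity measures. Nor does calling Day 0 the safety baseline exclude it for immunogenicity. Appendix 1 draws 80 mL for PBMC and plasma at Day 0, as at Weeks 4, 24 and 48, against 30 mL at screening, which points to Day 0. Not naming value or change is missing detail rather than a fault in the method.

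Finally, adjustment does not repair the non-randomised contrast. Period and assay-batch differences remain.

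**Conclusion.** The point holds as a low-cost efficiency gain to consider. It is not an error in the plan. Sections 8.3.2 and 8.3.3 give the collected baselines no part in the dose comparison, although 8.3.3 does use them for within-group change.

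The laboratory benefit is clear at moderate correlation (0.91 to 0.80 SD of change at r = 0.5), small at 0.8 to 0.9, and absent by about 0.95. It assumes equal SDs and a comparator t-test on change. The cAd3 benefit is nil to about two percentage points of power under the seroprevalence that the documents suggest. For GP, little or none is expected if baselines sit at the assay floor. That too is an assumption, though a plausible one because earlier filovirus and cAd3 vaccine recipients are excluded (Section 4.1.2).

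The documents do not support reading this as a faulty power statement, since 0.91 SD reproduces, or as a threat to the primary safety conclusions.

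**What to change.** In Section 8.3.2, add: *If continuous laboratory values are compared between groups, ANCOVA of the follow-up value on dose group and Day 0 value will be used, with the Wilcoxon rank sum test kept for clearly non-normal measures.*

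In Section 8.3.3, add: *The two-sample t-test at Week 4 will be accompanied by an ANCOVA of the Week 4 value (log scale for titres) on dose group and the pre-vaccination value of the same assay (Day 0 sample; for cAd3, the pre-vaccination neutralisation result). If no participant, or participants in only one group, are cAd3 seropositive before vaccination, the unadjusted result and a seronegative-only comparison will be reported. Baseline cAd3 immunity will be tabulated by group. The dose contrast will be described as non-randomised; adjustment does not remove period or assay-batch differences.*

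The 0.91 SD sentence in Section 8.2.1 stays as it is.

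The cost is a few lines of text and code, with no new samples, and about one degree of freedom (0.91 to 0.92 SD) if the covariate is uninformative. Because the groups are not randomised, adjusted and unadjusted results may differ if baselines differ. Reporting both immunogenicity results lets the reader see that.
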